Yet, LDCT screening for lung cancer is not without risks, most notably, radiation exposure and a high false-positive rate leading to subsequent follow-up and testing with its own associated harms. For the individual, the benefit of being screened for lung cancer with LDCT must be weighed against the potential harms: receiving false results, radiation exposure, and the risk of over diagnosis.[6, 9] A recent systematic review of evidence regarding the benefits and harms of LDCT screening for lung cancer confirmed the results of the NLST while raising concerns about the potential harms of screening.[10] The rate of positive results in each round of screening was 20% while only 1% of patients were found to have lung cancer. Overall, patients who completed all three screens had a 40% chance of having at least 1 abnormal result, requiring additional surveillance and diagnostic workup.

The need for patient decision aids to support informed decision making for lung cancer screening with LDCT is growing dramatically. Evidence-based guidelines have been released endorsing LDCT scans for high risk smokers, while emphasizing the importance of making an informed decision about screening within the context of receiving smoking cessation services for people who continue to smoke.[10, 11] We know from our preliminary study (Protocol PA11-0626) that patients are interested in the topic, know very little of lung cancer screening and the potential harms and benefits, and want decision support tools.[12] In addition, insurers are increasingly covering

LDCT scans for lung cancer screening among patients meeting criteria consistent with the NLST. The US Preventive Services Task Force has issued a guideline endorsing annual screening with LDCT.[13] If followed by Medicaid and Medicare coverage, this would greatly increase the pool of high risk individuals able to receive the scans without copays. Thus, lung cancer screening is rapidly becoming a viable secondary preventive service for many heavy smokers, and there is a great need for quality, evidenced-based patient decision support to help patients make informed screening decisions.

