We will also estimate actual screening rate (ASR) for lung cancer within each arm and

compare the ASRs between the two arms. We expect that approximately 300 participants will complete the 6-month follow-up assessment and provide information about completion of lung cancer screening (150/arm). A two group chi-square test with a 0.05 two-sided significance level will have 83% power to detect the difference between a ASR of 0.2 in Arm 2 and a ASR of 0.35 in Arm 1 (odds ratio of 2.154) when the sample size in each arm is 150.

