#### Analysis plan

Patients' demographic characteristics at baseline will be summarized using descriptive statistics such as mean, standard deviation, median, interquartile range (IQR), and frequency where appropriate. We will apply Student t-test/Wilcoxon test and Kruskal-Wallis test/analysis of variance (ANOVA) to compare continuous variables between arms, and the chi-square test or the Fisher's exact test to assess the differences of categorical variables between arms.[16]

As primary analysis, we will perform two-sided two group t-test to compare the differences of the three primary endpoints between the two arms. We will perform similar analysis on knowledge scores. For these efficacy endpoints, intend-to-treat analysis will be applied to the participants. We will look at the impact of race/ethnicity (African American vs. Caucasian) on the relationship between the outcomes and lung cancer screening materials using general linear regression. We will also assess the interaction between intervention and race/ethnicity using linear regression model to examine whether or not the decision aid has differential effects between African Americans and Caucasians by testing.

We will use two-sided two group t-test to compare the change of knowledge scores from baseline to post intervention between the two arms. Since the knowledge outcome will be assessed at week 1 and then 3-month and 6-month follow-ups, linear mixed effect models for longitudinal measures[17] will be employed to assess the change in the magnitude of the outcomes over time adjusting for multiple covariates including intervention indicator, age, gender, race, education level, insurance status, and other factors. We may also look at the interaction between intervention and time. Appropriate transformation of the measures will be used in the analyses to satisfy the normality assumption of linear mixed effect model. Mode of administration and completion of intervention/control materials (i.e., dose/exposure) will be tracked to account for their

effects.

We will also estimate the lung cancer screening rate within each arm along with 95% confidence interval. Chi-square test will be used to assess the differences of the lung cancer screening rates between arms.

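### Screening uptake: section 5.0 pre-specifies no between-arm difference with an interval, and the comparison leaves out state, age and insurance status

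*Combined protocol and SAP*

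**What the plan says.** Section 5.0, Analysis plan, gives two outputs for uptake. The first is descriptive: "We will also estimate the lung cancer screening rate within each arm along with 95% confidence interval". The second is the comparison: "Chi-square test will be used to assess the differences of the lung cancer screening rates between arms". The Justification of Sample Size describes the same pair and powers the test at a two-sided 0.05 level, with 150 per arm, where it "will have 83% power to detect the difference between a ASR of 0.2 in Arm 2 and a ASR of 0.35 in Arm 1". An odds ratio of 2.154 appears there, but only as a restatement of the planning rates. Neither subsection names a risk difference, risk ratio or odds ratio to be reported, or an interval for one.

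Age and insurance status are listed in the Analysis plan as covariates of the linear mixed model. That model is introduced for the repeated knowledge score and relies on normality, so it does not cover a binary outcome. State is the randomisation stratum (section 4.0, and Allocation Strategy in section 5.0) but does not enter the uptake comparison. The only general provision for adjustment, in section 4.0, concerns the delivery mode of the decision aid.

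Section 2.0 makes completion of screening exploratory and sets no a priori hypothesis for it.

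**The concern.** With no hypothesis about the direction or size of any change in uptake, a p-value answers little. The useful result is how many percentage points separate the arms and how uncertain that figure is. The plan gives an interval around each arm's rate and a test, but no interval around the contrast. Two separate intervals are a poor guide to a difference, because they can overlap when the test is significant.

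Leaving the measure unstated also leaves the scale (difference, ratio or odds ratio) and any adjustment open until the data are seen. State is a design factor, and the plan already treats age and insurance status as relevant covariates elsewhere. The Rationale links coverage to access: if Medicare and Medicaid follow the national guideline, "this would greatly increase the pool of high risk individuals able to receive the scans without copays". These are reasonable grounds for an adjusted estimate, though not evidence that adjustment would sharpen it.

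**Working it through.** **Inputs.** From the Justification of Sample Size: uptake 0.20 (Arm 2) and 0.35 (Arm 1), 150 per arm, two-sided alpha 0.05, stated power 83%, odds ratio 2.154. The documents give no association of age, insurance or state with uptake, so the values used in step 4 are assumptions.

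**1. The plan's own figure.** The pooled rate is 0.275.
- Null SE = √(2 × 0.275 × 0.725 / 150) = 0.05156.
- Alternative SE = √[(0.35 × 0.65 + 0.20 × 0.80) / 150] = 0.05083.
- Power = Φ[(0.15 − 1.96 × 0.05156) / 0.05083] = Φ(0.963) = 0.832.
- Odds ratio = (0.35/0.65) / (0.20/0.80) = 2.154.

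Both stated figures reproduce, without a continuity correction (with one, power is about 79.7%).

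**2. The interval the plan does not ask for.** At the planning rates, 0.15 ± 1.96 × 0.05083 gives 5.0 to 25.0 percentage points (Newcombe: 4.9 to 24.7), a half-width of about 10 points. On other scales the same data give a risk ratio of 1.75 (1.19 to 2.58) and an odds ratio of 2.15 (1.28 to 3.63). The plan does not say which would be reported.

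**3. Planned display against the difference interval (Wald, 150 per arm).**
- 30 v 45 events (20% v 30%): per-arm intervals are 13.6 to 26.4% and 22.7 to 37.3%, which overlap. The uncorrected chi-square p is 0.046. The difference interval is 10 ± 1.96 × 100 × √[(0.16 + 0.21)/150] = +0.3 to +19.7 points, which agrees with the test.
- 30 v 30 events: the difference interval is ± 1.96 × 100 × √(2 × 0.16/150) = ±9.1 points.

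**4. What adjustment might add.** Take the variance as multiplied by (1 − R²), with f = √(1 − R²). Half-width = 1.96 × 0.05083 × f, and power = Φ[(0.15 − 1.96 × 0.05156 × f) / (0.05083 × f)].

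| Assumed R² | Half-width (points) | Power |
|---|---|---|
| 0 | 10.0 | 83.2% |
| 0.02 | 9.9 | 84.0% |
| 0.05 | 9.7 | 85.1% |
| 0.10 | 9.5 | 86.9% |

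Simulation of a Mantel-Haenszel test stratified on a binary coverage variable (40,000 runs per setting) shows how far the gain depends on the assumption:
- 50 to 70% covered, coverage odds ratio for uptake 3 to 8: about 83–84% unadjusted, 85–89% stratified.
- 50 to 70% covered, odds ratio 2: a gain of about 0.6 points.
- 50 to 70% covered, odds ratio 1.5: essentially no gain.
- 90% covered, odds ratio 3: 83.7% to 83.8%.

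**The case against.** The strongest reply is that nothing is lost. Both rates will be reported, the difference is a subtraction, and its interval follows from the rates and arm sizes. Uptake is exploratory, outside the three primary outcomes and the secondary knowledge outcome, and unadjusted rates with a chi-square test are a legitimate analysis of a binary outcome in a randomised trial. All of this stands and limits the point to pre-specification.

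The documents do not support four stronger inferences that a reader might draw:

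- **That the plan cannot say how far the aid moves uptake.** It can, by the derivation just described.
- **That it demonstrably loses precision.** No association with uptake is given. The Rationale's remark on coverage is a conditional statement about policy. The age range of 55 to 77 was set to match the CMS coverage guideline, so coverage may be common, and age is itself restricted. The gain could be close to nil.
- **That overlapping intervals, or a non-significant test, will be read as no effect.** The plan assigns the comparison to the test and says nothing about either reading, so a general caution about non-significance is not needed.
- **That 150 per arm could not exclude a large shift.** At 20% in both arms, ±9.1 points excludes the 15-point planning difference.

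**Conclusion.** The point holds as a low-priority improvement. For uptake, the plan fixes neither a between-arm effect measure with an interval nor any use of the randomisation stratum or the covariates it lists for knowledge. The missing interval is the main part, with a half-width of about 10 points at the planning rates. That figure assumes the planned rates and about 150 respondents per arm.

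The covariate part is secondary. A gain of about 1 to 4 points of power (half-width 9.9 to 9.5 instead of 10.0) rests on an assumed R² of 0.02 to 0.10. The planned chi-square test and its 83% power are sound as stated.

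**What to change.** In section 5.0, Analysis plan:

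1. Keep the per-arm rates and the chi-square test. Add the between-arm risk difference in uptake with its 95% CI, and name the interval method.
2. Add a supporting estimate: a risk difference standardised over the analysed participants, from a logistic model with arm, state, age and insurance status. Standardising matters because the model's own odds ratio is a conditional quantity and differs from the unadjusted one. Pool small states by a rule fixed in advance: at the planning rates about 0.275 × 300 = 82.5 events are expected, too few for many state terms.

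The cost is a few sentences and one extra model. Age, insurance status and state are already in the plan, and the sample size does not change.

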## **6.0 Data Security and Confidentiality**

We are requesting a Data Safety Monitoring Board waiver on the grounds that this protocol presents no more than minimal risk to human subjects. The principal investigator (PI) will monitor the study. The research involves no procedures for which written consent is normally required outside of the research context. There is no medical or clinical intervention and no foreseeable risk of physical or economic harm. Possible psychological and social harms, which include worry about lung cancer and stigma associated with current or former smoking behavior, are no greater than the risks the subjects would encounter in their daily lives.

To protect confidentiality of the study participants, a unique study identification (ID) number will be assigned as an identifier. Subjects' participation in this study will be confidential and all data will be collected and coded in a confidential manner. The following data security procedures will be followed:

1. Collection of identifiers: Identifiers (name and contact information) will be collected but will be replaced by study ID numbers in the analytic file. The master database file that links the study ID to the participants' identifiers will be maintained on a secured server at MD Anderson in a password-protected file. The master database file will be accessible only to the principal investigator and those individuals on the delegation of authority log authorized to recruit and screen subjects for eligibility, consent, and collect data.
2. Data report: All data will be reported in aggregate format.
3. Training of personnel: Study personnel will be trained to maintain the confidentiality of personally-identifying information. All of the study personnel will complete the institution's human subjects protection training.
4. Data Storage: Data will be stored on password-protected computers behind the institution firewall and in REDCap. Data on password-protected computers will include these identifiers: name, address, telephone numbers, and email addresses. The only identifiers stored in REDCap will be ZIP codes. Data will not be transferred to laptop computers that are removed from the institution. Paper records will be retained by the principal investigator (PI) in locked files.
5. Data Sharing: Study data will not be shared with any individuals or entities that are not involved in the study. Protected health information (PHI) will not be reused or disclosed to any other person or entity, or for other research.
6. Final Disposition of Study Records: These data will be used only for this research study. Identifiers on password-protected computers including the key linking the study ID to the identifiers will be destroyed within 3 years of completion of the study. De-identified data on password-protected computers will be retained indefinitely. Data in REDCap will be archived rather than destroyed, including ZIP codes.

### REDCap

Study data will be managed using REDCap (Research Electronic Data Capture) electronic data capture tools hosted at MD Anderson.[19] REDCap ([www.project-redcap.org](http://www.project-redcap.org)) is a secure, web-based application with controlled access designed to support data capture for research studies, providing: 1) an intuitive interface for validated data entry; 2) audit trails for tracking data manipulation and export procedures; 3) automated export procedures for seamless downloads to common statistical packages; and 4) procedures for importing data from external sources. In the case of multi-center studies REDCap uses Data Access Groups (DAGs) to ensure that personnel at each institution are blinded to the data from other institutions. REDCap (<https://redcap.mdanderson.org>) is hosted on a secure server by MD Anderson Cancer Center's Department of Research Information Systems & Technology Services.

REDCap has undergone a Governance Risk & Compliance Assessment (05/14/14) by MD Anderson's Information Security Office and found to be compliant with HIPAA, Texas Administrative Codes 202-203, University of Texas Policy 165, federal regulations outlined in 21CFR Part 11, and UTMDACC Institutional Policy #ADM0335. Those having access to the data file include the study PI and research team personnel. Users are authenticated against MDACC's Active Directory system. External collaborators are given access to projects once approved by the project sponsor. The application is accessed through Secure Socket Layer (SSL). All protected health information (PHI) will be removed from the data when it is exported from REDCap for analysis. All dates for a given patient will be shifted by a randomly generated number between 0 and 364, thus preserving the distance between dates. Dates for each patient will be shifted by a different randomly generated number. Following publication study data will be archived in REDCap.

## **7.0 Informed Consent**

After initial screening for eligibility, subjects will be consented. We propose to obtain informed consent from patients via telephone using a verbal consent script (attached as a specialized informed consent). The CORE registration list will serve as a verbal consent log for accrual tracking. We are requesting a waiver of written authorization for the study (attached as a waiver of informed consent). We have used this approach in other educational research projects and patients find it highly acceptable. Patients will be given the option of participating in subsequent phases of this study or other research studies with an optional procedure for consent to recontact.

Since this protocol involves no more than minimal risk and does not involve the administration of drugs, radiotherapy, use of surgery, invasive procedures, or investigational devices, authority to obtain informed consent is delegated to individuals on the research staff who are not physicians. These individuals may include Professors, Instructors, Sr. Research Scientists, Postdoctoral Fellows, Program Coordinators, Clinical Studies Coordinators, Research Data Coordinators, Research Data Management Assistants, and Graduate Research Assistants who have completed Human Subjects Research Training.

